8.4. Multiplicity Adjustment

No multiplicity adjustment will be performed since the study has one primary efficacy endpoint with one primary population and analysis method. Sensitivity analyses for the primary efficacy endpoint are supportive and analyses for other efficacy endpoints are exploratory.

8.5. Data Safety Monitoring Board

An independent DSMB will periodically review a limited set of unblinded safety tables and/or listings, including all reported AEs. The objectives of the DSMB meetings are to review the safety outcomes of the study and provide guidance to the study sponsor regarding the safety of VM202. The data analyses for the DSMB meetings will be directly provided to the DSMB members and no data will be released to the study sponsor and blinded designees. There will be no adjustment for multiple testing due to the DSMB data reviews. The DSMB may be asked to review and provide guidance regarding protocol deviations that may affect the determination of the PP populations. Further details of DSMB responsibilities are included in the DSMB Charter.

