3.4.7. RANDOMIZATION AND BLINDING

A randomization schedule with subjects allocated to VM202 (treatment) or placebo (control) in a 2:1 ratio will be used.

The Pharmacist will review the subject's treatment allocation and assigned kit number in IWRS. All documents related to investigational product and treatment allocation will be kept in a secure location with access limited to Pharmacy personnel responsible for preparing the syringes with assigned study treatment.

After study initiation, VM202 and VM202 vehicle (placebo) will be provided to the site's pharmacy. Depending on the assigned study treatment, syringes of VM202 or placebo will be prepared after the clinic notifies the Pharmacy that the subject has arrived in the clinic to undergo study treatment.

This is a double-blind study. The patients, Investigators, study site staff, or Sponsor or any of the Sponsor's representatives or vendors will not know the assigned treatment. Blinding will be achieved by having the study medication (VM202) prepared by the study pharmacist or designee. Reconstituted VM202 is indistinguishable from VM202 vehicle (placebo). The site pharmacist or designee prepares the vials according to the instructions. The site pharmacist or designee and select individuals at the CRO (but excluding blinded study monitors and the blinded clinical trial manager) will be unblinded to the treatment assignments. The subject and study personnel, including core labs, principal investigator, co-investigators, study coordinators, study monitors, data managers, and the clinical trial manager will remain blinded until all data have been entered into the database and the database is locked.

IN CASE OF EMERGENCY ONLY, i.e., SERIOUS ADVERSE EVENT (SAE) AND ONLY WHEN THIS INFORMATION INFLUENCES THE SUBJECT'S

MANAGEMENT AND WHEN KNOWLEDGE OF THE TREATMENT ASSIGNMENT IS ESSENTIAL TO THE WELFARE OF THE PATIENT, the Investigator or designee may request unblinding of that patient. Whenever feasible, the Sponsor (or the Sponsor's representative) should be consulted in advance of breaking the blind for any patient. In any case, the Sponsor (or the Sponsor's representative) must be notified of the unblinding, and the Investigator or designee will document the reason(s) necessary to break the blind for any patient. Complete instructions on this process are detailed in the Study Reference Manual (VMNHU-003 Subject Emergency Unblinding Communication Plan).

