7.4. Per Protocol (PP) Populations

The first Per Protocol population is a subset of the mITT. It includes all mITT subjects who meet the following criterion:

• Have not used the protocol-specified prohibited concomitant medications such as COX-2 inhibitor drug(s) or non-specific COX-1/COX-2 inhibiting NSAIDS, anti-VEGF agents (e.g., Lucentis[®], Avastin[®], Eylea[®]), steroids (except inhaled steroids or ocular steroids), Regranex[®] gel (becaplermin), larval debridement, skin substitutes (e.g., Dermagraft[®], Apligraf[®]), hyperbaric oxygen therapy, hydrotherapy, negative pressure wound therapy, or electrical stimulation therapy which may affect the wound healing. The use and effect of protocol-specified prohibited concomitant medications will be determined by the CDRC in a blinded fashion prior to analyses.

The second Per Protocol population is a further subset of the mITT. It includes all subjects in the first PP population who also meet all of the following criteria:

- Meets major protocol eligibility criteria determined by the CDRC in a blinded fashion prior to analyses
- Received all injections based on the randomized treatment
- Maintained standard of care for their wounds for the duration of the study, as follows:
 - O Surgical debridement of necrotic tissue or devitalized tissue
 - Use of appropriate off-loading when ambulating
 - o Maintenance of moist wound environment
- Additional criteria, if any, established by the CDRC before unblinding of the randomization code

The PP populations will be used in the sensitivity analyses for the primary efficacy endpoint.

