8.3. Unmasking of Randomization Codes

For the final data analyses, the randomization code will be unmasked to the project team after all the data queries related to the efficacy and safety outcomes have been resolved and the corresponding data revisions have been completed in the database.

The randomization code for individual safety data will be unmasked to the DSMB members and the team that will prepare the unblinded summary tables for the DSMB meetings. However, in order to prevent bias, the unblinded detailed safety data summaries and listings will not be shared with the sponsor management team, the CDRC, the study sites, or the team that is monitoring the clinical data collection.

The randomization code will be unmasked to the team that will prepare the interim futility analysis described in Section 10. These unmasked primary efficacy results and the conditional power will be shared with unblinded Regulatory and Clinical advisors (to be named) and may be shared with the sponsor management team. However, in order to prevent bias, the unmasked interim results will not be shared with the CDRC, the study sites, or the team that is monitoring the clinical data collection.

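### SAP 8.5 lets a DSMB that holds treatment codes be asked for guidance on deviations affecting Per Protocol membership, which SAP 7.4 largely reserves for blinded decision

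*SAP*

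**What the plan says.** **Who decides Per Protocol (PP) membership.** SAP 7.4 defines PP1 by absence of prohibited medications or therapies: "The use and effect of protocol-specified prohibited concomitant medications will be determined by the CDRC in a blinded fashion prior to analyses". PP2 is a subset of PP1 with four further conditions. The eligibility condition reads "Meets major protocol eligibility criteria determined by the CDRC in a blinded fashion prior to analyses". Any additional conditions must come from the CDRC before the code is broken. For the other two, receipt of all injections and maintenance of standard wound care, the SAP names no assessor and does not mention blinding.

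**Who holds the code.** SAP 8.3: "The randomization code for individual safety data will be unmasked to the DSMB members". The same section protects the CDRC: "the unblinded detailed safety data summaries and listings will not be shared with the sponsor management team, the CDRC" or certain other parties, and it gives prevention of bias as the reason.

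**What the DSMB does.** SAP 8.5: "An independent DSMB will periodically review a limited set of unblinded safety tables and/or listings, including all reported AEs". It then adds: "The DSMB may be asked to review and provide guidance regarding protocol deviations that may affect the determination of the PP populations". Protocol 6.3.5 describes safety objectives only and, like SAP 8.5, leaves further detail to the DSMB Charter.

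**When the code is opened.** SAP 8.3 says that for the final analyses "the randomization code will be unmasked to the project team after all the data queries" on efficacy and safety outcomes are resolved and the resulting data revisions made. Protocol 3.4.7 keeps a list of study personnel blinded "until all data have been entered into the database and the database is locked".

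**What the PP sets are for.** They support sensitivity analyses of the primary endpoint (SAP 7.4, 9.4.1.2.2). The primary analysis uses all randomized subjects (SAP 7.1, 9.4.1.1).

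**The concern.** A PP analysis is a credible check only if subjects are excluded without knowledge of their arm. The SAP recognises this by shielding the CDRC. SAP 8.5 then opens a route by which people who know individual assignments can advise on the same exclusions.

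The advice could carry outcome information as well as arm. The DSMB sees all reported AEs, and SAP 5.3.2 identifies new target-foot ulcers solely from AE data and amputations from a review of AE data that is meant to be blinded.

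Judgement is needed at several points. PP1 turns on the use and the effect of a prohibited treatment, which is a matter of discretion. The two PP2 conditions with no named assessor leave the most room for outside guidance. At stake is whether PP1 and PP2 can be read as unbiased support for the primary result.

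**Working it through.** The plan states no figure on this point, so the check is mainly a comparison of provisions.

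**Step 1. Set the provisions side by side.**

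| Matter | Decided by | Blinding stated |
|---|---|---|
| mITT: disqualifying pre-dose results (SAP 7.3) | CDRC | Blinded, prior to analyses |
| PP1: prohibited treatments (SAP 7.4) | CDRC | Blinded, prior to analyses |
| PP2: major eligibility (SAP 7.4) | CDRC | Blinded, prior to analyses |
| PP2: additional criteria (SAP 7.4) | CDRC | Before unblinding |
| PP2: all injections received (SAP 7.4) | Not named | None stated |
| PP2: standard of care maintained (SAP 7.4) | Not named | None stated |
| Guidance on deviations affecting PP (SAP 8.5) | DSMB, if asked | None stated; members hold codes (SAP 8.3) |

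The last row conflicts with the PP1, PP2-eligibility and PP2-additional rows. For the two unassigned rows there is a gap, not a contradiction.

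**Step 2. Look for a provision that resolves it.** SAP 8.1 sends questionable data to the CDRC for blinded review, and SAP 9.5.6 has the CDRC choose the medications of interest that define the PP sets. Both confirm the CDRC's role. Neither requires DSMB guidance to be masked, to be given before any unblinded review, or to come from members without the code.

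**Step 3. Timing.** Protocol 3.4.7 uses database lock for the personnel it lists. SAP 8.3 uses query resolution and completed revisions, for an undefined project team, and mentions neither lock nor a final population list. Of the CDRC determinations in SAP 7.3 and 7.4, only the additional PP2 criteria are tied to unblinding; the others are tied to the start of analysis.

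**Step 4. Possible size of bias (illustration).** SAP section 1 gives enrolment of 7 + 5 + 16 + 16 = 44. Assume a 29:15 split (close to 2:1), no true effect, and the same responder rate p in both arms, 20% to 40%. Suppose k VM202 non-responders are excluded because their arm and outcome are known. The expected VM202 rate becomes 29p/(29 − k), so the difference shifts from zero by p × k/(29 − k):

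- k = 2: 2/27 = 0.0741. The shift is 1.5 points at p = 0.20, 2.2 at 0.30 and 3.0 at 0.40.
- k = 4: 4/25 = 0.16. The shift is 3.2, 4.8 and 6.4 points.

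The two-sided Fisher rejection rate in these cases, by exact enumeration, stays between 0.029 and 0.049, because the test is conservative at this size. The risk is a biased PP estimate more than a false-positive PP test.

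**Step 5. Sensitivity to one exclusion (all counts assumed).** Start from 16/29 against 4/15, which gives Fisher p = 0.111.

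| Subject removed | Table | p |
|---|---|---|
| Placebo responder | 16/29 v 3/14 | 0.052 |
| VM202 non-responder | 16/28 v 4/15 | 0.107 |
| VM202 responder | 15/28 v 4/15 | 0.116 |
| Placebo non-responder | 16/29 v 4/14 | 0.119 |

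Three of the four move p by less than 0.01, and none takes it below 0.05. A properly blinded exclusion would move p by exactly as much. The table shows how fragile 44 subjects are; it does not measure any effect of the DSMB.

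**The case against.** The best defence is that SAP 8.5 gives the DSMB no decision. It may be asked, it offers guidance, and the deviations concerned are ones that may affect membership. The CDRC keeps every criterion that SAP 7.4 assigns to it. The Charter might require masked deviation listings, and the protocol's silence about a PP role is weak evidence because it too refers to the Charter. PP results are supportive (SAP 8.4), and they are not the only robustness checks: SAP 9.4.1.2 also plans an ITT logistic regression and an mITT analysis. With 44 of the planned 300 subjects and the study stopped early, PP tests are unlikely to carry a conclusion.

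Most of this stands and limits the point. It does not remove it. Advice from someone who holds the code can bias a decision that someone else formally takes, and the SAP itself states no safeguard.

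On timing, a reader might infer a flat contradiction between the SAP and the protocol. The documents do not go that far. Protocol 3.4.7 lists particular roles and allows selected CRO staff to be unblinded, while SAP 8.3 leaves its project team undefined. The SAP wording is looser than lock and worth aligning, but it is a secondary matter and does not involve the DSMB.

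**Conclusion.** The point holds in limited form. SAP 8.5 is inconsistent with the blinded determination in SAP 7.4 and with the purpose of the shield in SAP 8.3. The exposure is confined to PP1 and PP2; the ITT primary test and its two-sided 0.05 level are untouched.

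Two stronger readings are tempting and not supported. One is that the unblinded DSMB decides PP membership; the text makes its role optional and advisory. The other is that a single DSMB-influenced exclusion would bring the PP result to the edge of significance. That rests on invented counts and on the most extreme of four possible exclusions.

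The 1.5 to 6.4 point range depends on the assumed 29:15 split, equal responder rates of 20–40%, and deliberate removal of two to four VM202 non-responders. It shows what could happen and predicts nothing about this trial. The conclusion also assumes that the unseen Charter does not already require masked review.

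**What to change.** 1. Delete the sentence on protocol deviations from SAP 8.5.
2. State in SAP 7.3 and 7.4 that the blinded CDRC alone rules on every deviation affecting mITT, PP1 and PP2. Include the two PP2 conditions that now have no assessor: receipt of all injections and maintenance of standard care.
3. As a secondary alignment with Protocol 3.4.7, amend SAP 8.3 so that the project team is unmasked only after database lock and a signed, dated CDRC list of mITT, PP1 and PP2 membership.
4. Check the DSMB Charter for matching text and bring it into line.

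The cost is SAP wording and one CDRC sign-off before unmasking, which SAP 7.3 and 7.4 already largely imply. Sample size, power, alpha and trial conduct do not change.

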8.6. Handling of Missing and Incomplete Data

Subjects may have missing specific data points for a variety of reasons. In general, data may be missing due to a subject's early withdrawal from study, a missed visit, or a clinical parameter not measured at a particular point in time. The general procedures outlined below describe how missing data are handled.

8.6.1. Missing Values for the CWIQ

No imputation for missing item scores within the CWIQ Overall Quality of Life will be performed; if a Quality of Life question (item) is unanswered at a subject's visit then the Overall Quality of Life score will be missing for that visit. Missing individual item scores within the three CWIQ domains may be imputed using the average score across the non-missing items within the domain at a subject's visit provided that the proportion of missing items scores within that domain is less than 25%; otherwise the domain score at that visit is missing. Thus, at least 11 of 14 items in the social life domain, 6 of 7 items in the well-being domain, and 19 of 24 items in the physical symptoms and daily living domain must be non-missing to avoid having a missing corresponding domain score.

8.6.2. Missing / Unknown Values of Covariates

For categorical covariates, the missing / unknown values will be combined with the category with the most subjects if the missing / unknown rate is $\leq 2\%$ of the pooled data and will be classified into a separate category if the missing / unknown rate is $\geq 2\%$ of the pooled data. If the covariate is also used as a subgrouping variable, the imputed values of the subgrouping variable will not be used for subgroup categorization.

8.6.3. Missing Dates and Times

If a start or stop date for an adverse event or a concomitant medication is completely missing, it will not be imputed. If that date is partially missing, imputed dates specified in Table 6 will be used to derive the duration of the adverse event or the duration of the medication use. If the start or stop date for an adverse event is not missing but the corresponding time is partially or completely missing, imputed times specified in Table 7 will be used to derive the duration of the adverse event. For adverse event attribution relative to a specific injection, a missing start date and time should default to the date and time of the immediately documented prior injection. Missing years will not be estimated under any conditions.

Table 6 Imputation Rules for Partial Adverse Event or Concomitant Medication Start and Stop Dates

	Missing	IMPUTATION	EXCEPTION
Start Date	Day	01	Default to Study Day 0 (day of first injection procedure) if an event starts in the same year and month as Study Day 0
	Day/Month	01JAN	Default to Study Day 0 if an event starts in the same year as Day 0
Stop Date	Day/Month	Last day of the month	Default to the End of Study Date if the imputed event stop date is after the End of Study Date or before start day of the event
	Day/Month	31DEC	Study Date or before start day of the event

Table 7 Imputation Rules for Partial or Missing Adverse Event Start and Stop Times

	Missing	IMPUTATION	EXCEPTION
Start Time	Minute	00	Default to time of first injection if an event
	Hour: Minute	00:00	starts on Study Day 0
Stop Time	Minute	59	(none)
	Hour: Minute	23:59	Default to 23:59 on the End of Study Date if
			the imputed event stop date is after the End
			of Study Date or before start day of the event

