3.7. PRIOR AND CONCOMITANT MEDICATION

All concomitant medications (taken within 60 days of the first injection) will be recorded at each study visit. For each medication taken, the following information will be collected:

- Medication trade name:
- Indication for which the medication was given;
- Dose/strength, route, and frequency of administration;
- Date started and date stopped (or continuation at study exit).

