9.5.6. Prior and Concomitant Medications

Prior medications are those medications taken within 60 days of the first injection of study drug. Concomitant medications are those medications taken on or after the day of the initial dose of study drug. All prior and concomitant medications will be assigned preferred drug names using WHODDE. Prior and concomitant medications of interest will be determined by the CDRC and will be used to define the per-protocol populations.

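### SAP Table 6 applies to medications a Day 0 start default that suits only adverse events, so drugs washed out before Day 0 can get false on-study or negative durations

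*SAP*

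**What the plan says.** SAP 8.6.3, Table 6, is titled "Imputation Rules for Partial Adverse Event or Concomitant Medication Start and Stop Dates", so medications are within its scope. The text above it gives the purpose: "imputed dates specified in Table 6 will be used to derive the duration of the adverse event or the duration of the medication use". Completely missing dates are left missing.

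- **Start, day missing:** first of the month, except "Default to Study Day 0 (day of first injection procedure) if an event starts in the same year and month as Study Day 0".
- **Start, day and month missing:** 1 January, except "Default to Study Day 0 if an event starts in the same year as Day 0".
- **Stop:** last day of the month, or 31 December, except "Default to the End of Study Date if the imputed event stop date is after the End of Study Date or before start day".

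Protocol 3.7 brings pre-treatment drugs into the record: "All concomitant medications (taken within 60 days of the first injection) will be recorded at each study visit". Protocol 3.2 has prohibited drugs washed out before the Day 0 injections. The washout periods in Protocol Appendix 3 are mostly one or two weeks, and 30 days for anti-VEGF agents. SAP 9.5.6 separates prior from concomitant use by date relative to the first dose, and adds: "Prior and concomitant medications of interest will be determined by the CDRC and will be used to define the per-protocol populations". Under SAP 7.4, PP1 excludes users of prohibited medications as determined by the CDRC under blind, and PP2 is nested in PP1.

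**The concern.** The Day 0 default is reasonable for adverse events. Protocol 5.2 and 5.3 collect them only after the first administration and send earlier events to medical history, so an event with a vague date cannot properly start before Day 0.

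Medications are different by design. The record reaches back 60 days, and a washed-out drug has both its start and its stop before Day 0. Table 6 makes no exception for a drug known to have ended by then. Its two exceptions also compound each other: the first moves the start forward to Day 0, and the second sees a stop earlier than that artificial start and replaces it with the End of Study Date. A record showing that the subject stopped the drug as required becomes an interval covering the whole study.

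The derived duration of medication use is what goes wrong directly. At one remove, the per-protocol sensitivity analyses of the primary endpoint could be affected if anyone used these intervals to decide who took a prohibited drug on study.

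**Working it through.** The plan states no figure for this rule, so there is none to reproduce. The check applies Table 6 literally.

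**Inputs.** The rules are those of SAP Table 6. The calendar dates are assumed for illustration. End of Study is taken as Day 0 + 210, from the Day 210 visit. Duration is counted inclusively as stop − start + 1, because the SAP gives no formula. In the available text both stop-date rows are labelled as day and month missing; the first is read as day missing only.

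**Example, step by step.** Day 0 is 15 Nov 2018, so End of Study is 15 Nov 2018 + 210 = 13 Jun 2019. A prohibited drug has its start recorded as 2018 and its stop as Oct 2018.

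1. The start year equals Day 0's year, so the start becomes 15 Nov 2018.
2. The stop becomes 31 Oct 2018, which is 15 days before that start.
3. The stop is imputed and precedes the start, so it is reset to 13 Jun 2019.
4. The interval runs from Day 0 to Day 210. True on-study use is 0 days.

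**Other combinations.** Every drug below truly ended before Day 0. Day 0 is 15 Jun 2019 and End of Study 11 Jan 2020, except in the second row (15 Mar 2019 and 11 Oct 2019).

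| Recorded start | Recorded stop | Table 6 interval | Days | Result |
|---|---|---|---|---|
| 2019 | May 2019 | 15 Jun 2019 to 11 Jan 2020 | 211 | False, Day 0 to End of Study (true use 10 to 20 May, 11 days) |
| 2019 | 2019 | 15 Mar to 11 Oct 2019 | 211 | False, Day 0 to End of Study (31 Dec falls after End of Study) |
| 2019 | 2019 | 15 Jun to 31 Dec 2019 | 200 | False on-study use, not to End of Study |
| 2019 | 20 May 2019 | 15 Jun to 20 May 2019 | −26 + 1 = −25 | Reversed; the stop is complete, so no reset applies |
| Jun 2019 | 5 Jun 2019 | 15 Jun to 5 Jun 2019 | −10 + 1 = −9 | Reversed |
| Jun 2019 | Jun 2019 | 15 to 30 Jun 2019 | 16 | False on-study use, not to End of Study |
| May 2019 | May 2019 | 1 to 31 May 2019 | 31 | Correctly before Day 0 |
| 2018 | May 2019 | 1 Jan 2018 to 31 May 2019 | 516 | Correctly before Day 0; the start is not moved |
| 10 May 2019 | 2019 | 10 May to 31 Dec 2019 | 236 | False on-study use from the stop rule alone |

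The full Day 0 to End of Study interval therefore needs both dates partial, with the start in Day 0's year (or month, if only the day is missing) and the imputed stop either before Day 0 or after End of Study. The last row shows that a year-only stop can mislead even when the start is complete, so a correction to the start rule alone is not enough.

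**Scale, if a subject were wrongly excluded.** SAP section 1 gives 7 + 5 + 16 + 16 = 44 enrolled. If all were randomised, one subject is 1/44 = 2.3% of ITT. The documents give no count of partial-date records.

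**The case against.** A reader might infer that Table 6 removes compliant subjects from PP1 and PP2. The documents do not support that.

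- SAP 8.6.3 names duration as the use of imputed partial dates. Where the SAP wants its imputation rules used for something else, it says so: SAP 9.5.3 makes attribution of adverse events to an injection subject to 8.6.3. SAP 7.4 and 9.5.6 contain no such reference.
- PP1 exclusion is a blinded CDRC judgement of both use and effect, and SAP 8.1 refers questionable values to the same committee. In the step-by-step example the record itself says the drug stopped in the month before Day 0.
- SAP 9.5.6 plans no summary of medication duration, so no named table receives the wrong interval.

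A reader might also infer that long-term users with vague start dates are the main group affected. They mostly are not, because a start recorded in an earlier calendar year is not moved.

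Sites are also well placed to record a washout stop in full. Protocol 3.4.4.1 has weekly screening visits that review medications, and Protocol 3.7 asks for stop dates. A complete stop gives a reversed interval, which an ordinary data check should catch. Finally, the exceptions speak of an event, so confining them to adverse events is an arguable reading already.

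All of this limits the consequence. It does not remove the defect: the table's title covers medications, Table 6 is the SAP's only date rule for them, and SAP 9.5.6 splits prior from concomitant use by date without saying whether reported or imputed dates apply.

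**Conclusion.** The point holds in limited form. Read literally, Table 6 gives a wrong duration of medication use for a washed-out drug whose partial start falls in Day 0's year or month. The error is about 210 false on-study days when a partial stop is imputed before Day 0, and a negative duration when the stop is complete and before Day 0.

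Wrongful loss from PP1, and hence PP2, is conditional on imputed dates being used for the prior/concomitant split or by the CDRC. How many records are affected is unknown. The PP analyses are supportive (SAP 7.4, 8.4), and the primary analysis is on ITT (SAP 7.1), so the primary result does not depend on this. Severity is minor. The day counts rest on the assumed calendar dates, End of Study at Day 210, and the reading of the first stop-date row as day missing.

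**What to change.** Amend SAP 8.6.3 and 9.5.6 as follows.

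1. In Table 6, restrict the Day 0 start exceptions, and the reset to End of Study when the stop precedes the start, to adverse events.
2. For medications, impute a missing start day as 01 and a missing day and month as 01JAN, never later than the recorded or imputed stop.
3. Treat a medication as prior when its recorded or partial stop shows that it ended before Day 0.
4. State that CDRC decisions on prohibited medication use rest on the dates as reported. Where a partial stop cannot be placed before or after Day 0, flag the record for CDRC review and do not settle it by imputation.

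In the step-by-step example this gives 1 Jan to 31 Oct 2018, correctly prior. A year-only stop in Day 0's year, or a stop known only to Day 0's month, would go to the CDRC under item 4. The cost is SAP wording and a small programming change before the CDRC review; no new data are needed.
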